### iRANO treatment algorithm for the assessment of progressive imaging findings in patients with neuro-oncological malignancies undergoing immunotherapy

CONFIDENTIAL

**15.4 Attachment: 4**

***Dose Modification or Discontinuation and Supportive Care Guidelines  
for Specific Drug-Related Adverse Events***

Gastrointestinal irAEs		
Severity of Diarrhea/Colitis (NCI-CTCAE v4)	Initial Management	Follow-up Management

Grade 1 Diarrhea: < 4 stools/day over Baseline Colitis: asymptomatic
	
Continue avelumab therapy Symptomatic treatment (e.g. loperamide)
	
Close monitoring for worsening symptoms Educate subject to report worsening immediately If worsens: Treat as Grade 2, 3 or 4.

Grade 2 Diarrhea: 4 to 6 stools per day over Baseline; IV fluids indicated < 24 hours; not interfering with ADL Colitis: abdominal pain; blood in stool
	
Withhold avelumab therapy Symptomatic treatment
	
If improves to Grade ≤ 1: Resume avelumab therapy  If persists > 5-7 days or recurs: Treat as Grade 3 or 4.

Grade 3 to 4 Diarrhea (Grade 3): ≥ 7 stools per day over Baseline; incontinence; IV fluids ≥ 24 h; interfering with ADL Colitis (Grade 3): severe abdominal pain, medical intervention indicated, peritoneal signs Grade 4: life-threatening, perforation
	
Withhold avelumab for Grade 3. Permanently discontinue avelumab for Grade 4 or recurrent Grade 3.  1.0 to 2.0 mg/kg/day prednisone IV or equivalent Add prophylactic antibiotics for opportunistic infections Consider lower endoscopy
	
If improves: Continue steroids until Grade ≤ 1, then taper over at least 1 month; resume avelumab therapy following steroids taper (for initial Grade 3).  If worsens, persists > 3 to 5 days, or recurs after improvement: Add infliximab 5mg/kg (if no contraindication). Note: infliximab should not be used in cases of perforation or sepsis.

CONFIDENTIAL

This material is the property of the NYU School of Medicine and Langone Medical Center. Do not disclose or use except as authorized in writing by the study sponsor

Dermatological irAEs		
Grade of Rash (NCI-CTCAE v4)	Initial Management	Follow-up Management
Grade 1 to 2 Covering ≤ 30% body surface area	Continue avelumab therapy Symptomatic therapy (for example, antihistamines, topical steroids)	If persists > 1 to 2 weeks or recurs: Withhold avelumab therapy Consider skin biopsy  Consider 0.5-1.0 mg/kg/day prednisone or equivalent. Once improving, taper steroids over at least 1 month, consider prophylactic antibiotics for opportunistic infections, and resume avelumab therapy following steroids taper. If worsens: Treat as Grade 3 to 4.
Grade 3 to 4 Grade 3: Covering > 30% body surface area; Grade 4: Life threatening consequences	Withhold avelumab for Grade 3. Permanently discontinue for Grade 4 or recurrent Grade 3. Consider skin biopsy Dermatology consult 1.0 to 2.0 mg/kg/day prednisone or equivalent Add prophylactic antibiotics for opportunistic infections	If improves to Grade ≤ 1: Taper steroids over at least 1 month; resume avelumab therapy following steroids taper (for initial Grade 3).
Pulmonary irAEs		
Grade of Pneumonitis (NCI-CTCAE v4)	Initial Management	Follow-up Management
Grade 1 Radiographic changes only	Consider withholding avelumab therapy Monitor for symptoms every 2 to 3 days Consider Pulmonary and Infectious Disease consults	Re-assess at least every 3 weeks If worsens: Treat as Grade 2 or Grade 3 to 4.
Grade 2 Mild to moderate new symptoms	Withhold avelumab therapy Pulmonary and Infectious Disease consults Monitor symptoms daily; consider hospitalization 1.0 to 2.0 mg/kg/day	Re-assess every 1 to 3 days If improves: When symptoms return to Grade ≤ 1, taper steroids over at least 1 month, and then resume avelumab therapy following steroids taper If not improving after 2 weeks or worsening: Treat as Grade 3 to 4.

**CONFIDENTIAL**

	
prednisone or equivalent Add prophylactic antibiotics for opportunistic infections Consider bronchoscopy, lung biopsy
	

Grade 3 to 4 Grade 3: Severe new symptoms; New/worsening hypoxia; Grade 4: Life-threatening
	
Permanently discontinue avelumab therapy. Hospitalize. Pulmonary and Infectious Disease consults. 1.0 to 2.0 mg/kg/day prednisone or equivalent Add prophylactic antibiotics for opportunistic infections Consider bronchoscopy, lung biopsy
	
If improves to Grade <math>\leq</math> 1: Taper steroids over at least 1 month If not improving after 48 hours or worsening: Add additional immunosuppression (for example, infliximab, cyclophosphamide, IV immunoglobulin, or mycophenolate mofetil)

Hepatic irAEs		
Grade of Liver Test Elevation (NCI-CTCAE v4)	Initial Management	Follow-up Management

Grade 1 Grade 1 AST or ALT <math>></math> ULN to 3.0 x ULN and/or Total bilirubin <math>></math> ULN to 1.5 x ULN
	
Continue avelumab therapy
	
Continue liver function monitoring If worsens: Treat as Grade 2 or 3 to 4.

Grade 2 AST or ALT <math>></math> 3.0 to <math>\leq</math> 5 x ULN and/or total bilirubin <math>></math> 1.5 to <math>\leq</math> 3 x ULN
	
Withhold avelumab therapy Increase frequency of monitoring to every 3 days.
	
If returns to Grade <math>\leq</math> 1: Resume routine monitoring; resume avelumab therapy. If elevation persists <math>></math> 5 to 7 days or worsens: Treat as Grade 3 to 4.

Grade 3 to 4 AST or ALT <math>></math> 5 x ULN and/or total bilirubin <math>></math> 3 x ULN
	
Permanently discontinue avelumab therapy Increase frequency of monitoring to every 1 to 2 days 1.0 to 2.0 mg/kg/day prednisone or equivalent Add prophylactic antibiotics for opportunistic infections Consult gastroenterologist/hepatologist Consider obtaining MRI/CT scan of liver and liver biopsy if clinically
	
If returns to Grade <math>\leq</math> 1: Taper steroids over at least 1 month If does not improve in <math>></math> 3 to 5 days, worsens or rebounds: Add mycophenolate mofetil 1 gram (g) twice daily If no response within an additional 3 to 5 days, consider other immunosuppressants per local guidelines.

CONFIDENTIAL

	warranted	
Renal irAEs		
Grade of Creatinine Increased (NCI-CTCAE v4)	Initial Management	Follow-up Management
Grade 1 Creatinine increased > ULN to 1.5 x ULN	Continue avelumab therapy	Continue renal function monitoring If worsens: Treat as Grade 2 to 3 or 4.
Grade 2 to 3 Creatinine increased > 1.5 and ≤ 6 x ULN	Withhold avelumab therapy Increase frequency of monitoring to every 3 days 1.0 to 2.0 mg/kg/day prednisone or equivalent. Add prophylactic antibiotics for opportunistic infections Consider renal biopsy	If returns to Grade ≤1: Taper steroids over at least 1 month, and resume avelumab therapy following steroids taper. If worsens: Treat as Grade 4.
Grade 4 Creatinine increased > 6 x ULN	Permanently discontinue avelumab therapy Monitor creatinine daily 1.0 to 2.0 mg/kg/day prednisone or equivalent. Add prophylactic antibiotics for opportunistic infections Consider renal biopsy Nephrology consult	If returns to Grade ≤1: Taper steroids over at least 1 month.
Cardiac irAEs		
Myocarditis	Initial Management	Follow-up Management
New onset of cardiac signs or symptoms and / or new laboratory cardiac biomarker elevations (e.g. troponin, CK-MB, BNP) or cardiac imaging abnormalities suggestive of myocarditis.	Withhold avelumab therapy. Hospitalize. In the presence of life threatening cardiac decompensation, consider transfer to a facility experienced in advanced heart failure and arrhythmia management. Cardiology consult to establish etiology and rule-out immune-mediated myocarditis. Guideline based supportive treatment as per cardiology consult.*  Consider myocardial biopsy if recommended per cardiology consult.	If symptoms improve and immune-mediated etiology is ruled out, re-start avelumab therapy.  If symptoms do not improve/worsen, viral myocarditis is excluded, and immune-mediated etiology is suspected or confirmed following cardiology consult, manage as immune-mediated myocarditis.

CONFIDENTIAL

Immune-mediated myocarditis	
Permanently discontinue avelumab. Guideline based supportive treatment as appropriate as per cardiology consult.* 1.0 to 2.0 mg/kg/day prednisone or equivalent Add prophylactic antibiotics for opportunistic infections.
	
Once improving, taper steroids over at least 1 month.
 
If no improvement or worsening, consider additional immunosuppressants (e.g. azathioprine, cyclosporine A).

-----------------------------	---	---

\*Local guidelines, or eg. ESC or AHA guidelines  
 ESC guidelines website: <https://www.escardio.org/Guidelines/Clinical-Practice-Guidelines>  
 AHA guidelines website:  
<http://professional.heart.org/professional/GuidelinesStatements/searchresults.jsp?q=&y=&t=1001>

Endocrine irAEs		
Endocrine Disorder	Initial Management	Follow-up Management

Grade 1 or Grade 2 endocrinopathies (hypothyroidism, hyperthyroidism, adrenal insufficiency, type I diabetes mellitus)
	
Continue avelumab therapy Endocrinology consult if needed
 
Start thyroid hormone replacement therapy (for hypothyroidism), anti-thyroid treatment (for hyperthyroidism), corticosteroids (for adrenal insufficiency) or insulin (for Type I diabetes mellitus) as appropriate.
 
Rule-out secondary endocrinopathies (i.e. hypopituitarism / hypophysitis)
	
Continue hormone replacement/suppression and monitoring of endocrine function as appropriate.

Grade 3 or Grade 4 endocrinopathies (hypothyroidism, hyperthyroidism, adrenal insufficiency, type I diabetes mellitus)
	
Withhold avelumab therapy Consider hospitalization Endocrinology consult
 
Start thyroid hormone replacement therapy (for hypothyroidism), anti-thyroid treatment (for hyperthyroidism), corticosteroids (for adrenal insufficiency) or insulin (for type I diabetes mellitus) as appropriate.
 
Rule-out secondary endocrinopathies (i.e. hypopituitarism / hypophysitis)
	
Resume avelumab once symptoms and/or laboratory tests improve to Grade <math>\leq</math> 1 (with or without hormone replacement/suppression).
 
Continue hormone replacement/suppression and monitoring of endocrine function as appropriate.

Hypopituitarism/Hypophysitis (secondary endocrinopathies)
	
If secondary thyroid and/or adrenal insufficiency is confirmed (i.e. subnormal serum FT4 with inappropriately low TSH and/or low serum cortisol with inappropriately
	
Resume avelumab once symptoms and hormone tests improve to Grade <math>\leq</math> 1 (with or without hormone replacement).
 
In addition, for hypophysitis with abnormal

CONFIDENTIAL

	
low ACTH):
 
 
Refer to endocrinologist for dynamic testing as indicated and measurement of other hormones (FSH, LH, GH/IGF-1, PRL, testosterone in men, estrogens in women)
 
Hormone replacement/suppressive therapy as appropriate
 
Perform pituitary MRI and visual field examination as indicated
 
 
If hypophysitis confirmed:
 
 
Continue avelumab if mild symptoms with normal MRI. Repeat the MRI in 1 month
 
Withhold avelumab if moderate, severe or life-threatening symptoms of hypophysitis and/or abnormal MRI. Consider hospitalization. Initiate corticosteroids (1 to 2 mg/kg/day prednisone or equivalent) followed by corticosteroids taper during at least 1 month.
 
Add prophylactic antibiotics for opportunistic infections.
 
	
MRI, resume avelumab only once shrinkage of the pituitary gland on MRI/CT scan is documented.
 
Continue hormone replacement/suppression therapy as appropriate.

Other irAEs (not described above)		
Grade of other irAEs (NCI-CTCAE v4)	Initial Management	Follow-up Management
Grade 2 or Grade 3 clinical signs or symptoms suggestive of a potential irAE	Withhold avelumab therapy pending clinical investigation	If irAE is ruled out, manage as appropriate according to the diagnosis and consider re-starting avelumab therapy If irAE is confirmed, treat as Grade 2 or 3 irAE.
Grade 2 irAE or first occurrence of Grade 3 irAE	Withhold avelumab therapy 1.0 to 2.0 mg/kg/day prednisone or equivalent Add prophylactic antibiotics for opportunistic infections Specialty consult as appropriate	If improves to Grade ≤ 1: Taper steroids over at least 1 month and resume avelumab therapy following steroids taper.

CONFIDENTIAL

Recurrence of same Grade 3 irAEs
	
Permanently discontinue avelumab therapy 1.0 to 2.0 mg/kg/day prednisone or equivalent Add prophylactic antibiotics for opportunistic infections Specialty consult as appropriate
	
If improves to Grade <math>\leq</math> 1: Taper steroids over at least 1 month.

Grade 4
	
Permanently discontinue avelumab therapy 1.0 to 2.0 mg/kg/day prednisone or equivalent and/or other immunosuppressant as needed Add prophylactic antibiotics for opportunistic infections Specialty consult.
	
If improves to Grade <math>\leq</math> 1: Taper steroids over at least 1 month


Requirement for 10 mg per day or greater prednisone or equivalent for more than 12 weeks for reasons other than hormonal replacement for adrenal insufficiency
 
Persistent Grade 2 or 3 irAE lasting 12 weeks or longer
	
Permanently discontinue avelumab therapy Specialty consult
	

Abbreviations: ACTH=adrenocorticotrophic hormone; ADL=activities of daily living; ALT=alanine aminotransferase; AST=aspartate aminotransferase; BNP=B-type natriuretic peptide; CK-MB=creatinine kinase MB; CT= computed tomography; FSH=follicle-stimulating hormone; GH=growth hormone; IGF-1=insulin-like growth factor 1; irAE=immune related adverse event; IV=intravenous; LH=luteinizing hormone; MRI=magnetic resonance imaging; NCI CTCAE=National Cancer Institute Common Terminology Criteria for Adverse Events; PRL=prolactin; T4=thyroxine; TSH=thyroid stimulating hormone; ULN=upper limit of normal.

**CONFIDENTIAL**

### **15.5 Attachment: 5**

#### ***Factors to Consider in Assessing the Relationship of AEs to Avelumab or Infusion Procedure, Study Procedure, or Combination Treatment***

Is there a reasonable possibility that the event may have been caused by the study drugs or infusion procedure, study procedure, or concomitant treatment?

**No:**

- due to external causes such as environmental factors or other treatment/s being administered
- due to the patient's/subject's disease state or clinical condition
- do not follow a reasonable temporal sequence following the time of administration of the dose of Avelumab, study procedure, or combination treatment
- do not reappear or worsen when dosing with Avelumab, study procedure, or combination treatment is resumed
- are not a known response to Avelumab or infusion procedure, study procedure, or combination treatment based upon pre-clinical data or prior clinical data

**Yes:**

- could not be explained by environmental factors or other treatment/s being administered
- could not be explained by the patient's disease state or clinical condition
- follow a reasonable temporal sequence following the time of administration of the dose of Avelumab
- resolve or improve after discontinuation of Avelumab, study procedure, or combination treatment
- reappear or worsen when dosing with Avelumab, study procedure, or combination treatment is resumed
- are known to be a response to Avelumab or the infusion procedure, study procedure, or combination treatment based upon pre-clinical data or prior clinical data

NOTE: This list is not exhaustive.

**CONFIDENTIAL**

**15.6 Attachment: 6**

**Technical Specifications and Structural Considerations for  
Planning Radiotherapy**

**Technique:**

Intensity modulated radiotherapy (IMRT) via any method (e.g., VMAT, static field IMRT) or Stereotactic Radiotherapy (SRT) is required. Protons are permitted for institutions which have been approved and credentialed for protons, as protons may reduce the volume of normal tissue which will be re-irradiated. If protons are used, to avoid delays resulting from unplanned equipment availability, photon therapy may be administered instead of proton therapy.

**Every attempt must be made to obtain the original radiotherapy treatment plan in order to guide re-irradiation treatment planning.**

**Dose Specifications**

Photons: Treatment shall consist of 25 Gy delivered in 5 fractions delivered over 5 consecutive treatment days. The treatments may extend over the weekend (e.g., 5 treatment days over 8 calendar days.) Target coverage and homogeneity limits and deviations are listed in **Table A1**.

Protons - Absorbed dose: Doses are expressed in units of RBE-weighted absorbed dose,  $D_{RBE}$ . For protons the RBE is taken to be 1.1.  $D_{RBE} = 1.1 \times D$ , where D represents the absorbed dose in Gy. Treatment shall consist of 25 Gy(RBE) delivered in 5 fractions. Target coverage and homogeneity limits and deviations are listed in the **Table A1** below.

**Table A1: Target Coverage and Dose Limits**

Dose Metric	Per Protocol	Variation Acceptable	Deviation Unacceptable
Volume of PTV covered by the prescription dose of 25 Gy photons - protons 25 Gy(RBE)	Greater than or equal to 95% of the PTV should receive greater than or equal to 25 Gy photons - protons 25 Gy(RBE)	Greater than or equal to 90% of the PTV receiving greater than or equal to 25 Gy photons - protons 25 Gy(RBE)	Less than 90% of the PTV receiving greater than or equal to 25 Gy photons - protons 25 Gy(RBE). Coverage less than 90% is acceptable in areas of OAR/PTV overlap.
Minimum dose to the PTV (0.03 cc)	Greater than or equal to 21.25 Gy (85% of the prescription dose) photons – protons 21.25 Gy(RBE)	Greater than or equal to 20 Gy (80% of the prescription dose) photons – protons 20 Gy(RBE); Minimum doses of less than 20 Gy are acceptable if they occur due to OAR/PTV overlap	Less than 20 Gy (80% of the prescription dose) photons – protons 20 Gy(RBE); Minimum doses of less than 20 Gy are unacceptable unless they occur in regions of OAR/PTV overlap
Maximum dose to the PTV (0.03 cc)	Less than or equal to 30 Gy (120% Rx Dose)	Less than or equal to 32.5 Gy (130% Rx	Greater than 32.5 Gy (130% Rx Dose)

CONFIDENTIAL

This material is the property of the NYU School of Medicine and Langone Medical Center. Do not disclose or use except as authorized in writing by the study sponsor

	photons – protons 30 Gy(RBE). For SRT, this represents a plan prescribed to the 84% or greater Isodose line)	Dose) photons – protons 32.5 Gy(RBE). For SRT, this represents a plan prescribed to the 80% isodose line)	photons – protons 32.5 Gy(RBE) or an isodose line less than 80% for a radiosurgical plan)
--	--	---	---

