### Treatment Planning/Target Volumes

A GTV will be defined using the CT and MRI images.

The GTV includes the post-operative resection cavity if no residual enhancing or non-enhancing tumor is noted. The GTV also includes any non-enhancing tumor as identified on T2/FLAIR. T2/FLAIR signal consistent with edema is not included in the GTV. Therefore a distinction is made between T2 edema (typically without mass effect, sparing the cortical ribbon, obeying the grey/white junction, etc.) with T2 tumor (mass effect with sulcal effacement, involvement of the grey/white junction, obliteration of the cortical ribbon). Care is made to not include any enhancement or T2 signal on the post-operative scan that is due to post-surgical infarct. Fusion of the pre-operative MRI to determine initial extent of the tumor is helpful.

A PTV expansion that is justified based on image guidance and immobilization will be applied. Regardless of immobilization and localization methods, the PTV expansion should be no larger than 3 mm. Therefore, for stereotactic treatment, the PTV is typically 1 mm. For non-stereotactic treatment with IGRT, then the PTV is typically 3 mm.

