### Critical Structures

Normal tissues to be contoured will include the brain, brainstem, optic nerves and chiasm. Planning risk volume (PRV) expansions the same size as the PTV expansion (e.g. If the PTV is 3 mm, then the PRV is 3 mm. For stereotactic machines, a PTV of 0 mm is acceptable; therefore the PTV = CTV = GTV + 5 mm in this instance) should be utilized for optic nerves and chiasm.

CONFIDENTIAL

This material is the property of the NYU School of Medicine and Langone Medical Center. Do not disclose or use except as authorized in writing by the study sponsor

Special consideration should be given to avoid doses greater than the prescription dose within the scalp as well as limiting the exit dose through the oral cavity and mucosa.

The treatment parameters should be modified to optimize the conformity of the prescription isodose volume to the target volume while minimizing dose to critical structures. OAR limits for newly diagnosed GBM are given in **Table A2**.

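### Table A1 equates a 32.5 Gy (130%) maximum with the 80% isodose line for SRT, but 80% is 31.25 Gy (125%), so SRT plans between the two doses score both acceptable and unacceptable

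*Combined protocol and SAP*

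**What the plan says.** Attachment 6 (Section 15.6) prescribes 25 Gy in 5 fractions, by IMRT or stereotactic radiotherapy (SRT). Protons are permitted at credentialed institutions.

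The maximum-dose row of Table A1 ("Maximum dose to the PTV (0.03 cc") has three compliance columns:

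- Per Protocol: at most 30 Gy, given as 120% of prescription. "For SRT, this represents a plan prescribed to the 84% or greater Isodose line".
- Variation Acceptable: at most 32.5 Gy, given as 130%. "For SRT, this represents a plan prescribed to the 80% isodose line".
- Deviation Unacceptable: above 32.5 Gy, "or an isodose line less than 80% for a radiosurgical plan".

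On target volumes, Treatment Planning/Target Volumes defines a gross tumor volume (GTV) and moves straight to the PTV: "the PTV expansion should be no larger than 3 mm". It adds that "for stereotactic treatment, the PTV is typically 1 mm", and that "For non-stereotactic treatment with IGRT, then the PTV is typically 3 mm". It names no CTV. Critical Structures, in a parenthesis about margins for organs at risk, allows a 0 mm PTV on stereotactic machines and continues: "therefore the PTV = CTV = GTV + 5 mm in this instance".

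**The concern.** Each cell of the maximum-dose row gives an SRT planner two tests, one in gray and one as an isodose line. In the first two columns the second test is worded as a translation of the first. If the translation is wrong in one column, the two tests disagree for some plans, and a compliance reviewer could grade the same plan either way. SRT is one of the two named techniques, and the equipment listed for the lead site includes a Gamma Knife unit, so this is not a hypothetical class of plan.

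The target-volume text raises a separate question of the same kind. A planner who reads only Treatment Planning/Target Volumes adds 1 to 3 mm to the GTV. A planner on a stereotactic machine who reads the Critical Structures parenthesis adds 5 mm. All patients have had prior CNS radiotherapy (Section 4.1, criterion 8), so the volume of brain re-irradiated should not depend on which paragraph is read.

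**Working it through.** **Isodose conversion.** Input: prescription 25 Gy (Attachment 6, Dose Specifications). When a plan is prescribed to an isodose line, maximum dose = 25 / line, and line = 25 / maximum dose.

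The table's first pair reproduces:

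- 120% × 25 = 30 Gy, and 25/30 = 83.3%.
- From the other side, 25/0.84 = 29.76 Gy (119.0%).

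So 84% or greater is a rounded-up match for 30 Gy, and the table is using the usual conversion.

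The second pair does not reproduce:

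- 130% × 25 = 32.5 Gy, as stated, but 25/32.5 = 76.9%, not 80%.
- 25/0.80 = 31.25 Gy, and 31.25/25 = 125%, not 130%.
- The gap is 32.5 − 31.25 = 1.25 Gy, or 5 percentage points of the prescription.

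Consequence within the row, for an SRT plan prescribed to the 78% line: maximum = 25/0.78 = 32.05 Gy. That is below 32.5 Gy, so the plan is Variation Acceptable by dose. It is also below the 80% line, so the plan is Deviation Unacceptable. The same holds for every maximum above 31.25 and up to 32.5 Gy, that is, for lines from 76.9% up to but not including 80%.

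**Target volume.** The documents give margins but no volumes, so a sphere is used for illustration: volume = (π/6) × (diameter in cm)³, with twice the margin added to the diameter. The GTV diameter is 4 cm, the largest not excluded by Section 4.2, criterion 8.

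- GTV + 1 mm (typical stereotactic): (π/6) × 4.2³ = 38.8 cc.
- GTV + 3 mm (typical non-stereotactic, and the cap): (π/6) × 4.6³ = 51.0 cc.
- GTV + 5 mm (the parenthesis, 0 mm PTV expansion): (π/6) × 5.0³ = 65.4 cc.

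Ratios: 65.4/38.8 = 1.7 and 65.4/51.0 = 1.3. Read literally, the stereotactic plan with no PTV expansion treats more tissue than the widest non-stereotactic plan.

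**The case against.** The best defense of Table A1 is that its isodose lines form a complete ladder for SRT: 84% or greater, then 80%, then below 80%. The unacceptable cell fails a plan on either test, so a careful reader applies the stricter one. Following the ladder never breaches a dose limit either, since 84% gives 29.76 Gy (within 30) and 80% gives 31.25 Gy (within 32.5). This stands as a description of how a cautious site would behave, and it is why the point is minor. It does not make the middle cell right, because that cell presents 80% as equivalent to 32.5 Gy and not as a separate, tighter limit.

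A second defense is that the maximum is taken over 0.03 cc while an isodose line refers to the point maximum. The 0.03 cc dose cannot exceed the point maximum, so at the 80% line it is at most 31.25 Gy. The distinction does not rescue the pairing. The documents give no figure for the difference, so none is used here for either column.

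On the target volume, a reader might infer that 5 mm breaks the 3 mm cap. The documents do not establish that: the cap is on the PTV expansion, and 5 mm may be a CTV step placed before it. A reader might also infer that a 5 mm CTV adds to the usual 1 or 3 mm PTV margin, with larger volume ratios. No section writes that combination. The only one written is GTV + 5 mm with a 0 mm PTV expansion.

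Safeguards also exist. The Table A2 limits for the brainstem and optic structures hold whatever the margin, and isodose distributions go to the overall PI, though only after treatment is complete.

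**Conclusion.** The 130%/80% pairing is an arithmetic error. It creates a band, maximum above 31.25 and up to 32.5 Gy, in which an SRT plan receives two contradictory compliance grades from one table row. This assumes that SRT and radiosurgical plan mean the same thing in that row, and that the 0.03 cc maximum equals the point maximum. Non-SRT plans are not affected. Attachment 6 says its dose constraints derive from an earlier re-irradiation trial whose specifications are not reproduced, so the documents cannot settle whether 80% or 130% was intended.

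The target-volume inconsistency is real but secondary. Its size is about 1.3- to 1.7-fold for the illustrative 4 cm sphere. Actual GTVs differ, since the section also counts non-enhancing tumor or the resection cavity.

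Severity is minor. The Simon design, alpha, power and sample size (Section 7.1.3) are unaffected. A reader might go further and conclude that the CNS toxicity halt in Section 3.4 is compromised; the documents give no relation between margin and toxicity, so that cannot be supported. Nor is it claimed that the analysis sets are untouched: Sections 5.2.1 and 7.3.1 make evaluability for dose-limiting toxicity in subjects without such an event depend on HFRT completed per protocol.

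**What to change.** In Table A1, for SRT plans, state 31.25 Gy (125%) with the 80% line in both the Variation Acceptable and Deviation Unacceptable columns. This keeps the stricter limit that the unacceptable column already applies. If the radiation oncologists intend 130%, state 32.5 Gy with 77% in both columns instead (25/0.77 = 32.47 Gy). Use one term, SRT or radiosurgical, throughout the row.

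In Treatment Planning/Target Volumes, state whether a 5 mm CTV applies and to which plans, and make the Critical Structures parenthesis match. That choice belongs to the sponsor's radiation oncologists.

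The cost is a wording change to Attachment 6.
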